6.2.1 Safety

Safety will be evaluated by:

- 1) Tracking adverse events reported by participants, and collected proactively in bi-weekly check-ins conducted by the research coordinator, as described below; and,
- 2) The unblinded research assistant will monitor symptoms recorded in participant's headache diaries for any unexpected changes in symptoms. Potential adverse events or any other situation requiring reaction management will immediately be reported to the PI. If [name] is unavailable, or if her role as PI would interfere with her ability to assess and intervene with participant distress, [name], Ph.D., clinical psychology and Director of Clinical Training at Ferkauf Graduate School of Psychology, Yeshiva University ([contact]) will assess and determine the best course of action in the case of participant distress.

The unblinded research assistant will collate data regarding adverse events and changes in symptoms by group and provide these data to the Data Safety Monitoring Committee monthly.

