6.2.1.2 Adverse Events Definition And Reporting

An adverse event (AE) is any troublesome medical occurrence in a subject during participation in the clinical study. An AE can include a sign, symptom, abnormal assessment, or any combination of these. A serious adverse event (SAE) is any AE that results in one or more of the following outcomes: death, a life-threatening event, inpatient hospitalization or prolongation of existing hospitalization, a persistent or significant disability/incapacity, a congenital anomaly or birth defect, or an important medical event based upon appropriate medical judgment. We will use the HHS/NIH/NCI Common Terminology Criteria for Adverse Events (Version 4.0) grading scale; for reference, we have provided the criteria for headache AEs (Grades 1-3): Grade 1: Mild (mild headache pain); Grade 2: Moderate (moderate headache pain that limits instrumental activities of daily living); Grade 3: Severe or medically significant but not immediately life threatening (severe headache pain that limits self-care activities of daily living); Grade 4: Life-threatening consequences; Grade 5: death related to AE. When present, each AE will be categorized according to the likelihood that they are related to the CDST on a 4-point scale, ranging from definitely unrelated, possibly related, probably related, to definitely related. The expected risk of the CDST intervention is increased headache activity due to inhibition of therapeutic choice of participants. This risk is considered minimal.

The research coordinator will assess adverse events in bi-weekly check-ins with participants. The unblinded research assistant will assess headache activity bi-weekly and provide reports to the Data Safety Monitoring Committee (DSMC) at minimum every 6 months. The research assistant will call participants at least once per month throughout the study to assess for adverse events. The PI will also monitor each participant's recorded headache diaries monthly to assess for adverse events.

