If any of these procedures identify a potential adverse event, the participant will be called immediately to assess the potential adverse event. Participants who disclose potential adverse events to any study staff at any point during the study will immediately be reported to the PI, [name], Ph.D., clinical psychologist. If [name] is unavailable, [name], Ph.D., clinical psychology and Director of Clinical Training at Ferkauf Graduate School of Psychology, Yeshiva University ([contact]) will assess and determine the best course of action in the case of immediate participant distress. If the adverse event requires medical or professional intervention, the PI or [name] will immediately contact the participant's primary clinician at the MHC and develop an intervention plan and referral if necessary. If a participant experiences an adverse event, he or she will be given an opportunity to leave the study. Any SAEs that are possibly related to the study intervention will be reported to the IRB and NIH within 7 days. All AEs will be compiled and reported to the Einstein IRB and NIH in accordance with the Einstein IRB requirements.

The Data Safety Monitoring Committee (DSMC) will consist of Drs. [name]., Assistant Professor of Psychology, and [name]., Professor of Psychology, at Ferkauf Graduate School of Psychology, Yeshiva University. The DSMC has final authority regarding making decisions regarding continuation, revision or discontinuation of the research project. The DSMC will meet every six months. The unblinded research assistant will provide reports of adverse events and diary-recorded symptoms by group to the DSMC at minimum every six months. The DSMC will provide minutes of each meeting to the PI, including attendance, summary of the discussion, and any findings. The PI will be responsible for implementation of this Data Safety Monitoring Plan and will report directly to the Einstein IRB and the NIH.

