Phase 3: At the end of Phase 2, a research assistant supervised by the PI will evaluate each participant’s diary data to determine eligibility criteria for Phase 3. The research coordinator will reach out to each participant and inform them of their eligibility determination for Phase 3, and assess interest in continuing in the study. Participants who are eligible and interested in participating in Phase 3 will be randomized by an unblinded research assistant, who will have no contact with participants after randomization. The rest of the study staff will be unaware of each participant’s randomization status.

After randomization, the participant will be sent instructions for initialization of the intervention study app from the research coordinator. Participants will use the intervention version of the app for three months. During this time, participants will continue to complete the headache diary three times daily and complete monthly and endpoint surveys (see Figure 6.3.1).

The research coordinator will continue to email each participant bi-weekly and provide feedback on diary days completed, offer troubleshooting for the application, and assess for adverse events, and reach out if the participant fails to record data for 2 days in a row. After the conclusion of Phase 3, the research coordinator will thank participants for their study participation and provide a compensation gift card (\$20 for Month 6 surveys, \$10 for Months 4 and 5 surveys, and \$0.50 for each diary entry, with total possible compensation of \$85).

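### Knowledge of arm can influence adverse event ascertainment and trial conduct: the unblinded assistant screens diaries without a set trigger, relatedness is defined only to the CDST, and DSMC minutes reach a blinded PI with no closed part

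*Combined protocol and SAP*

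**What the plan says.** **Who knows the arm.** Under section 6.3.1 Study Schedule, eligible participants are "randomized by an unblinded research assistant, who will have no contact with participants after randomization". The same section continues: "The rest of the study staff will be unaware of each" participant's assignment. On paper the PI and the research coordinator are therefore blind.

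**Who looks for events.** Section 6.2.1 Safety states: "The unblinded research assistant will monitor symptoms recorded in" the headache diaries, looking for symptom changes that were not expected. Sections 6.1.4 Reaction Management and 6.4.3.3 Safety give that person the same task. Sections 6.2.1.2 and 7.7 add a bi-weekly assessment of headache activity by the same person. Anything flagged goes upward: "Potential adverse events or any other situation requiring reaction management will immediately be reported to the PI". Sections 6.2.1.2 and 7.7 list other routes: the coordinator's bi-weekly check-ins, the PI's monthly reading of every diary, and monthly calls ("The research assistant will call participants at least once per month throughout the study to assess for adverse events").

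**How relatedness is rated.** Sections 6.2.1.2 and 7.8 say that "each AE will be categorized according to the likelihood that they are related to the CDST on a 4-point scale". They name no rater and give no equivalent scale for Headache Education or for study procedures.

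**What the DSMC sees and sends.** The unblinded assistant supplies "reports of adverse events and diary-recorded symptoms by group to the DSMC". Sections 6.2.1.2 and 7.7 then say: "The DSMC will provide minutes of each meeting to the PI, including attendance, summary of the discussion, and any findings".

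**The concern.** The protocol sets up blinding of everyone but one person, then leaves three openings in it.

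First, that one person exercises judgement about who has a potential adverse event. The protocol also tells the reader which arm to suspect, because sections 6.1.4, 6.2.1.2 and 7.8 name increased headache activity as the expected risk of the CDST.

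Second, the relatedness scale refers to a product that half the randomised participants do not receive.

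Third, a PI who is meant to be blind receives an account of discussions held over by-group data.

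Adverse events are a listed feasibility and acceptability outcome (section 5.2.2), and by-group event and symptom reports are what the DSMC is given when it decides whether the project continues. A flag also has consequences for the participant. Under sections 6.2.1.2 and 7.8 it prompts an immediate call, and a participant with an adverse event is offered the chance to leave. Flagging that depends on arm could therefore lead to contact and dropout that depend on arm.

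**Working it through.** The plan gives no event rate, threshold or test for adverse events, so there is no figure to reproduce. The check sets the sections side by side.

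1. **Room for discretion in diary screening.** Section 5.3.2 enrols people with 6 to 14 headache days per month, and the grading scale in section 6.2.1.2 starts at mild head pain. Headache is therefore frequent in both arms, and a screener must decide what is unexpected. Sections 6.1.4, 6.2.1 Safety and 6.4.3.3 set no rule such as a stated change from the participant's own Phase 2 level. The decision falls to the person who knows the arm.

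2. **How far the other routes protect.** The PI reads each diary monthly and the coordinator asks about events bi-weekly. Both are blind under section 6.3.1, and flagged events go to the PI. The unblinded assistant therefore proposes events and does not decide them. An arm-aware flag can still add cases to those assessed, and the blind routes cannot undo that selection.

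3. **Consequence of one extra departure.** Section 6.1.2 randomises 30 per group. One departure is 1/30 = 3.3% of an arm, so even a few arm-related departures would show.

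4. **Relatedness in the control arm.** Section 6.1 gives control participants the Headache Education version. A rater who knows this has to call every control event unrelated to the CDST. A rater who does not know must answer for a product the participant may not have. Section 3.3.1 Potential Risks lists discomfort from keeping the diary and from lifestyle education, and the CDST-only scale has no place for an event caused by the diary or by the control app. The seven-day rule for serious events in sections 6.2.1.2, 6.4.3.3 and 7.8 depends on relation to the study intervention, a wider term with no scale of its own.

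5. **Route from the DSMC to the PI.** The DSMC's input is by group. Its output to the PI covers the discussion and any findings. Sections 6.2.1.2, 7.7 and 7.8 mention no closed session, redaction or open summary. Diary symptoms are also efficacy data, since headache days and pain severity are secondary outcomes in section 5.2.2. The PI meanwhile supervises the Phase 3 eligibility check (section 6.3.1), reads diaries for events and assesses the events reported.

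6. **How often this could arise.** Section 5.1.1 allots 1 February 2018 to 1 October 2019, 20 months, to recruiting and running participants. Phase 3 cannot start until about three months after the first enrolment, which leaves about 17 months. With meetings every six months, 17/6 = 2.8, so two or three sets of minutes would fall within the randomised phase. The no-cost extension in section 7.12 suggests that the actual calendar ran longer.

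**The case against.** The case against making much of this is substantial, and much of it stands.

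- **Arm-blind routes exist.** The unblinded assistant is one screener among several and does not classify events. The DSMC also receives participant-entered diary symptoms, so its view does not rest on flags alone. A reader might infer that safety data are gathered differently in the two arms. The documents do not say so: the written procedures are the same for both, and differential flagging is only a possibility.
- **Relatedness can be judged blind.** A blind rater can ask whether the CDST could plausibly have caused an event without knowing who had it. A reader might infer that the control arm has no related events by construction. That holds only if the rater knows the arm, which is not stated. The practical reach is also limited: section 7.4 requires all serious events to be reported within seven days whatever their cause, and no planned analysis uses the rating. The lack of a defined meaning for control events remains.
- **The minutes are not said to contain by-group results.** This is correct. What is missing is a rule that keeps such results out.
- **The PI and the analysis.** A reader might infer that a partly unblinded PI would supervise the analysis. Sections 7.5.1.1 and 7.5.1.2 say only that lab members named as key personnel will carry it out.
- **The monthly caller.** A reader might see a breach of the no-contact rule for the randomising assistant. Section 6.2.1.2 mentions the unblinded assistant and then a research assistant in adjacent sentences, and section 7.5.1 uses the plural, so two people are the natural reading. One clarifying word is enough.
- **Scale.** This is a 60-person pilot of education apps with risk described as minimal. That limits the stakes, but the remedy is also small.

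**Conclusion.** The point holds as a weakness in safeguards; no bias has been demonstrated. Three gaps are in the text: an undefined trigger applied by an arm-aware screener, a relatedness scale tied to one arm with no named rater, and DSMC minutes to a blinded PI without an open and closed part. Through them, knowledge of arm can affect event ascertainment, event classification and trial conduct.

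The size cannot be calculated. The documents give no flagging rates, and any ratio of reported events would only restate rates chosen by the reader. The blind routes reduce the effect by an unknown amount. The primary adherence outcomes are entered by participants, and nothing here shows an effect on them.

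The conclusion assumes that blinding of the PI and coordinator under section 6.3.1 works as written. For the coordinator that is open to question, because the same section has that person send the app initialization instructions and troubleshoot the app. The change is worth making because it is cheap, but the study does not depend on it.

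**What to change.** Amend the protocol wording as follows.

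1. Assign diary surveillance to existing staff who are unaware of arm: the PI, and the coordinator if that person can be kept blind when sending and troubleshooting the app. State in advance one flagging rule based on change from the participant's Phase 2 diary, and apply it to both arms.
2. Limit the unblinded assistant to collating by-group tables for the DSMC.
3. Define relatedness to the assigned study app, either version, or to study procedures, and name a rater who is blind to arm.
4. Have the DSMC send the PI its recommendation and an open summary. Keep by-group discussion in a closed record until database lock, unless the DSMC judges that safety requires disclosure.
5. State that the assistant who makes the monthly calls is not the one who randomises.

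Two neighbouring inconsistencies should be reconciled in the same amendment: monthly DSMC data (sections 6.2.1 Safety and 6.4.3.3) against reports at least every six months (sections 6.2.1.2 and 7.7), and seven-day reporting of possibly related serious events (sections 6.2.1.2, 6.4.3.3 and 7.8) against all serious events (section 7.4).

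The cost is an amendment and a short flagging rule, with no new staff. The drawback is that the PI sees less interim detail; the safety exception in item 4 covers the case where that matters.

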6.2.1.2 Adverse Events Definition And Reporting

An adverse event (AE) is any troublesome medical occurrence in a subject during participation in the clinical study. An AE can include a sign, symptom, abnormal assessment, or any combination of these. A serious adverse event (SAE) is any AE that results in one or more of the following outcomes: death, a life-threatening event, inpatient hospitalization or prolongation of existing hospitalization, a persistent or significant disability/incapacity, a congenital anomaly or birth defect, or an important medical event based upon appropriate medical judgment. We will use the HHS/NIH/NCI Common Terminology Criteria for Adverse Events (Version 4.0) grading scale; for reference, we have provided the criteria for headache AEs (Grades 1-3): Grade 1: Mild (mild headache pain); Grade 2: Moderate (moderate headache pain that limits instrumental activities of daily living); Grade 3: Severe or medically significant but not immediately life threatening (severe headache pain that limits self-care activities of daily living); Grade 4: Life-threatening consequences; Grade 5: death related to AE. When present, each AE will be categorized according to the likelihood that they are related to the CDST on a 4-point scale, ranging from definitely unrelated, possibly related, probably related, to definitely related. The expected risk of the CDST intervention is increased headache activity due to inhibition of therapeutic choice of participants. This risk is considered minimal.

The research coordinator will assess adverse events in bi-weekly check-ins with participants. The unblinded research assistant will assess headache activity bi-weekly and provide reports to the Data Safety Monitoring Committee (DSMC) at minimum every 6 months. The research assistant will call participants at least once per month throughout the study to assess for adverse events. The PI will also monitor each participant's recorded headache diaries monthly to assess for adverse events.

If any of these procedures identify a potential adverse event, the participant will be called immediately to assess the potential adverse event. Participants who disclose potential adverse events to any study staff at any point during the study will immediately be reported to the PI, [name], Ph.D., clinical psychologist. If [name] is unavailable, [name], Ph.D., clinical psychology and Director of Clinical Training at Ferkauf Graduate School of Psychology, Yeshiva University ([contact]) will assess and determine the best course of action in the case of immediate participant distress. If the adverse event requires medical or professional intervention, the PI or [name] will immediately contact the participant's primary clinician at the MHC and develop an intervention plan and referral if necessary. If a participant experiences an adverse event, he or she will be given an opportunity to leave the study. Any SAEs that are possibly related to the study intervention will be reported to the IRB and NIH within 7 days. All AEs will be compiled and reported to the Einstein IRB and NIH in accordance with the Einstein IRB requirements.

The Data Safety Monitoring Committee (DSMC) will consist of Drs. [name]., Assistant Professor of Psychology, and [name]., Professor of Psychology, at Ferkauf Graduate School of Psychology, Yeshiva University. The DSMC has final authority regarding making decisions regarding continuation, revision or discontinuation of the research project. The DSMC will meet every six months. The unblinded research assistant will provide reports of adverse events and diary-recorded symptoms by group to the DSMC at minimum every six months. The DSMC will provide minutes of each meeting to the PI, including attendance, summary of the discussion, and any findings. The PI will be responsible for implementation of this Data Safety Monitoring Plan and will report directly to the Einstein IRB and the NIH.

6.3 Study Procedures

6.3.1 Study Schedule

Phase 1A

Screening and Enrollment: Up to 50 potential participants will be screened to identify 24 participants eligible and interested in the study. Potential participants will be contacted by phone or email by the research coordinator to be screened for inclusion criteria. If participants meet inclusion criteria and are interested in study participation, the research coordinator will provide informed consent over the phone (see "CDST stamped Oral Consent Form", previously approved).

Study Procedures: Participants will then receive an email from the research coordinator (see "CDST - App download email" attached) with instructions to download the study app. Participants will download the study app onto their device and will receive either the CDST or Headache Education version of the app. Participants will use the app, including three daily diary entries, for one week. After one week, the PI will have conduct a focus group interview with each participant (see "Focus Group Seed Questions 11.10.15" previously approved). Once the focus group is completed, the research coordinator will send the participant a thank you email (see "CDST - Thank you emails "attached) with an attached gift card compensation (\$30).

[figure not shown]
Phase 1B

Screening and Enrollment: Up to 500 potential participants will be screened to identify 250 participants eligible and interested in the study. Potential participants may be contacted by phone or email by the research coordinator to be screened for inclusion criteria. If participants meet inclusion criteria and are interested in study participation, they will provide informed consent via the REDCap app.

Study Procedures: Participants will then receive an email from the research coordinator (see “CDST - App download email” attached) with instructions to download the study app. Participants will download the study app onto their device. Participants will use the app, making one daily diary entry, for one month. After one month, the PI may conduct a focus group interview with each participant (see “Focus Group Seed Questions 11.10.15” previously approved). Once participation completed, the participant will be entered in a raffle for one of three \$200 gift cards as compensation.

Phase 2 and 3

Figure 6.3.1. Phase 2 and 3 Study Schedule

Screening: Up to 350 participants will be screened to identify 120 participants who may be eligible to participate in Phase 2 of the study. The research coordinator will identify participants who may be eligible using Clinical Looking Glass. The PI will obtain permission from providers with numerous potentially eligible patients to send a letter from the provider informing them of their eligibility for the study and providing them study contact information to opt-out of further communication, or express interest in enrollment (see “CDST Recruitment Potential Participant Letter” previously approved). Participants will then be contacted by phone or email (see “CDST - Introductory email to participants” attached) by the research coordinator to set up phone screens with a research assistant, who will be supervised by the PI (see “Phase 2-3 Screening Checklist 1.8.18” attached).

Phase 2: Participants who are interested in study participation and self-report meeting eligibility criteria during the phone screen will be sent a REDCap link to provide informed consent and complete baseline surveys (see Figure 6.3.1). Participants who provide informed consent and complete all Month 0 surveys will be sent instructions to initialize the study app for daily diary data collection ONLY (e.g., no CDST or Headache Education intervention). Participants will complete one month of daily diary collection during the Baseline Evaluation Period to assess eligibility criteria that require diary confirmation. If participants continue to meet criteria for the study, they will be invited to complete monthly and midpoint assessments and continue with the daily diary until Month 3.

The research coordinator will email each participant bi-weekly and provide feedback on diary days completed, offer troubleshooting for the application, and assess for adverse events (see “CDST - Bi-weekly email” attached). Participants will receive an additional contact from the research coordinator if they fail to record data for 2 days in a row (see “CDST - Missed entries email” attached). After the conclusion of Phase 2, the research coordinator will thank participants for their study participation (see “CDST - Thank you emails” attached) and provide a compensation gift card (\$20 for Month 0 and 3 surveys, \$10 for Months 1 and 2 surveys, and \$0.50 for each diary entry, with total possible compensation of \$105).

Phase 3: At the end of Phase 2, a research assistant supervised by the PI will evaluate each participant’s diary data to determine eligibility criteria for Phase 3. The research coordinator will reach out to each participant and inform them of their eligibility determination for Phase 3, and assess interest in continuing in the study. Participants who are eligible and interested in participating in Phase 3 will be randomized by an unblinded research assistant, who will have no contact with participants after randomization. The rest of the study staff will be unaware of each participant’s randomization status.

After randomization, the participant will be sent instructions for initialization of the intervention study app from the research coordinator. Participants will use the intervention version of the app for three months. During this time, participants will continue to complete the headache diary three times daily and complete monthly and endpoint surveys (see Figure 6.3.1).

The research coordinator will continue to email each participant bi-weekly and provide feedback on diary days completed, offer troubleshooting for the application, and assess for adverse events, and reach out if the participant fails to record data for 2 days in a row. After the conclusion of Phase 3, the research coordinator will thank participants for their study participation and provide a compensation gift card (\$20 for Month 6 surveys, \$10 for Months 4 and 5 surveys, and \$0.50 for each diary entry, with total possible compensation of \$85).

